8.2.2.3 Prior data conflict

Prior data conflict will be investigated for all informative priors through use of graphical displays. If there is evidence of prior data conflict for a given parameter, then a vague prior will be used for that parameter.

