If necessary, the results of any planned DMC and/or interim analysis may be shared with key Sponsor's personnel in order to facilitate additional Clinical Planning or Portfolio Management decisions. The results will include both individual and summary results, and will be presented unblinded. All individuals seeing unblinded data will be documented in the Trial Master File.

Further details are provided in the study manuals and site blinding plan.

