15.11 Planned interim analysis and data monitoring

This study will include two unblinded interim analyses, the first after approximately 45 subjects have completed 4 weeks of the study and the second when the last randomized subject for this study has completed the Week 12 Visit at the end of the Treatment Period or this subject's participation has ended prematurely. The purpose of these interim analyses is for sponsor key personnel to review results from the primary efficacy analysis and a subset of the analyses of exploratory efficacy and safety outcomes to facilitate additional Clinical Planning or Portfolio Management decisions; consequently, neither analysis will lead to any formal decision to alter or terminate the trial. Interim analyses will be conducted by an unblinded study team and will follow internal SOPs for the formal process to control the unblinding of the study for interim analysis purposes. This process will ensure that no unnecessary or unintentional unblinding occurs. The unblinded team will not disclose any unblinded information to the blinded study team and the storage of all unblinded documentation will be held securely and separately from the rest of the study documentation and outputs up until the end of the study. All analyses and unblinding instructions will be prespecified in the interim SAP and SAP.

The conduct of the study and monitoring of the safety data will be supervised by an independent DMC to optimize subjects' safety and to identify any safety signals. Full details of the DMC composition and roles will be described in a separate DMC Charter.

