3.4 Protocol deviations

Important protocol deviations (IPDs) are deviations from the protocol which potentially could have a meaningful impact on the primary objective of the study. The criteria for identifying such protocol deviations will be defined within the IPD document which is part of the data cleaning plan. Important protocol deviations will be classified as follows:

- Inclusion/exclusion criteria deviations
- Administration of prohibited concomitant medications
- Deviations relating to withdrawal criteria
- Visit schedule deviations

- Study drug administration deviations (including incorrect treatment received, handling and storage deviations and incorrect dosage received)
- Treatment non-compliance
- Procedural non-compliance
- Missing data
- Other

Important protocol deviations will be reviewed as part of the ongoing data cleaning process and data evaluation.

At least 3 data evaluation meetings (DEMs) will be performed for this study at the following time points:

- Prior to the informal unblinded interim analysis planned after approximately 45 subjects have completed 4 weeks of the study.
- Prior to the informal unblinded interim analysis planned after the last subject (excluding 2 subjects from site 101 in Australia who entered the study outside of the original planned recruitment period) has completed 12 weeks of the study or has discontinued early.
- Prior to the final analysis after all subjects have completed the SFU period and data have been verified/coded/entered into the database

Additional DEMs may be conducted as deemed necessary.

The purpose of these DEM reviews will be to review all protocol deviations, define the analysis sets, and check the quality of the data. The reviews will also help decide how to manage problems in the subjects' data (eg, missing values and withdrawals).

Accepted deviations from theoretical time points will be described in the appropriate documents and included in the Study Master File. After the pre-analysis review, resolution of all issues, and documentation of all decisions (including inclusion into each of the analysis sets) at the final DEM, the database will be locked.

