4.5.2 Interim analysis

This study will include two informal unblinded interim analyses, the first after approximately 45 subjects have completed 4 weeks of the study and the second when the last randomized subject for this study has completed the Week 12 Visit at the end of the Treatment Period or this subject's participation has ended prematurely. This second planned interim analysis excludes the 2 subjects from site 101 who entered the study outside of the recruitment period. The purpose of these interim analyses is for sponsor key personnel to review results from the primary efficacy analysis and a subset of the analyses of exploratory efficacy and safety outcomes to facilitate additional Clinical Planning or Portfolio Management decisions. Neither interim analysis will lead to any formal decision to alter or terminate the trial.

Details on the summaries and analyses to be presented at these informal interim analyses are included in the Interim Analysis SAP.

All analyses and unblinding instructions will be pre-specified in the Interim Analysis SAP.

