8.2.2.1 Bayesian modeling

The primary Bayesian model (a logistic regression model for the mean binary response $E[y]$) will be:

$$\ln\left(\frac{E(y)}{1-E(y)}\right) = \beta_{PBO} X_{PBO} + \beta_{BKZ} X_{BKZ} + \beta_{ADA} X_{ADA} + \beta_{hII} X_{hII} + \beta_{hIII} X_{hIII} \quad (1)$$

where X_{PBO} , X_{BKZ} and X_{ADA} are dummy variables taking the value 1 or 0 according to whether or not each subject is in the PBO, BKZ or ADA treatment groups respectively, X_{hII} and X_{hIII} are dummy variables taking the value 1 or 0 according to whether or not each subject is in the Baseline Hurley Stage II or III groups respectively. Proof-of-concept (PoC) will be declared in this study if the estimated posterior probability, using the above model, of the difference in response rates between the BKZ and PBO treatment groups is 0.975 or greater.

For parameter estimation, the following constraint will be used:

$$\beta_{hII} = -\beta_{hIII}$$

giving the model:

$$\ln\left(\frac{E(y)}{1-E(y)}\right) = \beta_{PBO} X_{PBO} + \beta_{BKZ} X_{BKZ} + \beta_{ADA} X_{ADA} + \beta_{hII} (X_{hII} - X_{hIII}) \quad (2)$$

so that the influence of Baseline Hurley Stage on the model estimated treatment group mean responses are more evident. To see this, note that if $\bar{\eta}_{PBO}$ represents the mean of the logit responses from model (2) for the PBO subjects (the simple “arithmetic” mean) then $\text{logit}^{-1}(\bar{\eta}_{PBO})$ is the response probability associated with that mean logit response and is 1 type of estimate of the PBO group response rate. Accordingly:

- $p_{PBO} | p_{hII}^{PBO}, p_{hIII}^{PBO} = \text{logit}^{-1}(\bar{\eta}_{PBO}) = \text{logit}^{-1}(\beta_{PBO} + \beta_{hII}(p_{hII}^{PBO} - p_{hIII}^{PBO}))$ represents the probability of response in the PBO group conditional on p_{hII}^{PBO} and p_{hIII}^{PBO} , which are the Baseline Hurley Stage subject proportions chosen to evaluate the estimated PBO group mean at (here the observed proportions are chosen)
- $p_{BKZ} | p_{hII}^{BKZ}, p_{hIII}^{BKZ} = \text{logit}^{-1}(\bar{\eta}_{BKZ}) = \text{logit}^{-1}(\beta_{BKZ} + \beta_{hII}(p_{hII}^{BKZ} - p_{hIII}^{BKZ}))$ represents the probability of response in the BKZ group conditional on p_{hII}^{BKZ} and p_{hIII}^{BKZ} which are the Baseline Hurley Stage subject proportions chosen to evaluate the estimated BKZ group mean at (here again the observed proportions are chosen)

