If the observed Baseline Hurley Stage effects and/or subject proportions in the proposed study are very different from those in the PIONEER II study then, and in addition to the possible invalid estimates of β_{PBO} and β_{ADA} , the estimated treatment group response rates may no longer reflect those in the data since the means of the probability scale priors will no longer match the treatment group response rate means in the observed data.

Both informative priors in (5) have been heavily discounted to account for study to study variation in both the ADA and PBO response rates, and also uncertainty in the agreement between the subject proportions and effect sizes observed in the Baseline Hurley Sage groups in the PIONEER II study and this proposed study.

To protect against severe forms of study to study variation and/or mismatches between Baseline Hurley Stage subject proportions and effect sizes, prior data conflict will be investigated for all informative priors through use of graphical displays. If there is evidence of prior data conflict for a given parameter, then a vague prior will be used for that parameter. Investigating any prior data conflict also provides some protection against model misspecification – for example if there turns out to be a Baseline Hurley Stage by treatment group interaction as the PIONEER II data suggest.

To be consistent with models used in previous UCB studies which parameterize PBO as the model intercept with the active treatment being additive effects (on the logit scale) we note that model (2) can be re-parameterized as follows:

$$\begin{aligned}\beta_{PBO} &= \gamma_{PBO} & (6) \\ \beta_{ADA} &= \gamma_{PBO} + \gamma_{ADA} \\ \beta_{BKZ} &= \gamma_{PBO} + \gamma_{BKZ} \\ \beta_{hII} &= \gamma_{hII}\end{aligned}$$

giving the model

$$\ln\left(\frac{E(y)}{1-E(y)}\right) = \gamma_{PBO} + \gamma_{BKZ} X_{BKZ} + \gamma_{ADA} X_{ADA} + \gamma_{hII}(X_{hII} - X_{hIII}) \quad (7)$$

Using this model, the process of mapping the informative priors in (5) to the logit coefficients is:

$$\begin{aligned}\beta_{PLB} &= \text{logit}(p_{PBO}) & (8) \\ \beta_{ADA} &= \text{logit}(p_{ADA}) \\ \gamma_{ADA} &= \beta_{ADA} - \beta_{PBO} \\ \gamma_{BKZ} &= \beta_{BKZ} - \beta_{PBO}\end{aligned}$$

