8.2.3.4 Vague prior distribution

A sensitivity analysis will be performed to investigate the influence of the choice of prior distribution on the results of the primary analysis. This will be performed and results reported using the same methodology as described in [Section 8.2.2.4](#) but assuming vague priors for all Beta distributed parameters of the model (ie, Beta [0.5, 0.5]).

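### The SAP makes the primary proof-of-concept model drop an informative prior when graphs show conflict with the data, but gives no objective trigger and does not say whether staff who saw unblinded interim results may make that call

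*SAP*

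**What the plan says.** SAP 8.2.2.1 defines the logistic model and ties the decision to it: "Proof-of-concept (PoC) will be declared in this study if the estimated posterior probability, using the above model", with a threshold of 0.975 for bimekizumab over placebo. The placebo prior is Beta(5.52, 14.48) and the adalimumab prior is Beta(11.78, 8.22). SAP 2.4 puts each at about 20 subjects, the size of each concurrent arm.

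The same section says that, as protection against severe study-to-study variation or Hurley-stage mismatch, "prior data conflict will be investigated for all informative priors through use of graphical displays". SAP 8.2.2.3 gives the consequence: "If there is evidence of prior data conflict for a given parameter, then a vague prior will be used for that parameter". The swap is therefore mandatory once conflict is seen. Neither section says what counts as evidence.

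Other relevant text:
- SAP 8.2.3.4 gives Beta(0.5, 0.5) as the vague prior for the all-vague sensitivity analysis.
- SAP 3.1 assigns statistical evaluation to the contract research organization, with oversight and supervision by the sponsor.
- SAP 4.5.2 plans two unblinded interim analyses for "sponsor key personnel to review results from the primary efficacy analysis". The second covers all randomized subjects except 2. Protocol 7.9 says of results shared with key sponsor personnel: "The results will include both individual and summary results, and will be presented unblinded".
- Protocol 15.11 separates the teams: "The unblinded team will not disclose any unblinded information to the blinded study team".
- Protocol 15.5.1 contains no conflict-triggered swap, and SAP 3.9 does not list one among its changes to the protocol-defined analyses.

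**The concern.** The check compares this study's placebo and adalimumab responses with their priors, so it can only be made on response data by arm. Its result fixes which prior stands behind the 0.975 criterion. With only a visual standard, two careful statisticians could read the same plot differently and reach opposite PoC verdicts on identical data.

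Other changes to the priors are protected. SAP 8.2.2.2 limits updates from external information to the period before unblinding, and bars use of this study's response rates when updating for Hurley proportions. Neither safeguard can apply to the conflict check. By the final analysis, some sponsor staff will have seen unblinded primary results from all but 2 subjects, and the SAP does not say whether they may take part in reading the graphs.

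**Working it through.** **Inputs.** Arms of 40 bimekizumab and 20 placebo; planned rates 70% and 27.6%; threshold 0.975 (SAP 2.4). Placebo prior Beta(5.52, 14.48); bimekizumab prior N(0, 10000) on the logit scale (SAP 8.2.2.1). Replacement prior Beta(0.5, 0.5) (SAP 8.2.3.4).

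**Assumptions.** No Hurley term and full arms. The SAP has no measure of conflict, so I use the two-sided prior-predictive tail: p(x) = 2 × min{P(X ≤ x), P(X ≥ x)}, with X beta-binomial(20, 5.52, 14.48).

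**Method.** For each pair (x placebo, y bimekizumab responders), compute P(bimekizumab > placebo) by numerical integration and declare PoC if it is at least 0.975. Then sum Bin(20, pP) × Bin(40, pB) over all 21 × 41 outcomes.

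**The plan's own figure.** With the informative prior always kept, PoC probability at 27.6% vs 70% is 98.7%, against at least 99% in SAP 2.4. The simplified model reproduces it closely.

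**Which placebo counts are ambiguous.** p is 0.026 at 0 responders, 0.110 at 1, 0.271 at 2, 0.292 at 9, 0.172 at 10, 0.095 at 11 and 0.048 at 12. Hence:
- a 5% trigger flags 0 or ≥12;
- a 10% trigger flags 0 or ≥11;
- a 20% trigger flags ≤1 or ≥10.

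**What the choice of prior does.** Bimekizumab responders needed out of 40:

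| Placebo responders | p | Informative prior | Beta(0.5, 0.5) |
|---|---|---|---|
| 10/20 | 0.172 | 25 | 30 |
| 11/20 | 0.095 | 26 | 32 |

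At 11/20, any bimekizumab count from 26 to 31 passes with one prior and fails with the other. The swap can also favour success: 0/20 against 6/40 gives 0.563 with the informative prior and 0.976 with Beta(0.5, 0.5).

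**How often the verdict changes.** For p between 5% and 10% the only count is 11/20, so the frequency is P(X_P = 11) × P(26 ≤ X_B ≤ 31), where the second factor is about 0.70 at 70%.
- 27.6% vs 70%: 0.65% × 0.70 ≈ 0.45%.
- 40% vs 70%: 7.1% × 0.70 ≈ 4.9%.

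For a looser zone of 5% to 20% (counts 1, 10 and 11), the frequencies are 1.5% and 11.7%.

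**Operating characteristics by trigger** (false PoC means both arms share the same true rate):

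| Scenario | No swap | 5% | 10% | 20% | Always vague |
|---|---|---|---|---|---|
| PoC, 27.6% vs 70% | 98.7% | 98.6% | 98.1% | 97.1% | 90.4% |
| PoC, 40% vs 70% | 93.4% | 89.9% | 84.9% | 78.2% | 63.4% |
| False PoC, both 27.6% | 1.2% | 1.3% | 1.3% | 1.8% | 2.4% |
| False PoC, both 50% | 13.0% | 12.6% | 12.0% | 10.7% | 2.7% |

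**The case against.** The strongest reply is that the harm is limited. The SAP aims the check at severe departures, so 10/20 placebo responders (p = 0.172) would hardly qualify and the grey zone is narrow. That stands, and it is why the 5% to 10% zone leads here. The all-vague analysis is also pre-specified, so readers will see whether PoC survives without borrowing. That stands in part. The SAP does not say which result decides in a borderline case, and once a swap occurs no section requires the informative-prior result to be shown.

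A reader might infer stronger points that the documents do not support:
- **That no replacement prior exists.** Beta(0.5, 0.5) is in SAP 8.2.3.4 and is the natural reading. Using N(0, 10000) instead under a 5% trigger leaves the PoC probabilities unchanged to two decimals.
- **That nobody is responsible and no time is set.** SAP 3.1 assigns the analysis, and the check is a step within it. Its absence from the data evaluation meetings is expected, because they precede unblinding: "The purpose of these DEM reviews will be to review all protocol deviations, define the analysis sets, and check the quality of the data".
- **That interim results were used to steer the prior.** Nothing says so, and Protocol 15.11 keeps the teams apart. The gap is only that the SAP does not apply this separation to the conflict check.
- **That the open trigger greatly inflates false PoC.** Varying the trigger between 5% and 20% moves it from 1.3% to 1.8% at a common 27.6%. At a common 50% the high rate comes from the borrowing itself, and a swap lowers it.

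**Conclusion.** The point holds and should be fixed, at modest weight. A mandatory change of prior inside the model that decides PoC depends on a visual judgement of arm-level response data, and the SAP neither sets a trigger nor says whether people with interim knowledge may make that judgement.

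At the planned rates the effect is small: PoC probability stays between 97.1% and 98.6% across the three triggers. It becomes material if placebo response is well above 27.6%, which is one of the situations the check is meant for. At 40% vs 70% the range is 78.2% to 89.9%.

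These figures rest on full arms of 40 and 20, no Hurley term, and my choice of the prior-predictive tail as the measure of conflict. In that simplified model the adalimumab swap affects only the informal comparison with bimekizumab. The Interim Analysis SAP, which Protocol 15.5.2 says will also document the priors, was not available. If it holds a rule, what remains is a missing cross-reference.

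**What to change.** Before final unblinding, with wording agreed by staff who have no access to interim results, amend SAP 8.2.2.3 as follows:

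1. Set one numeric prior-predictive rule for each informative prior. An example is two-sided p < 0.05, which flags 0 or ≥12 of 20 placebo responders and ≤5 or ≥18 of 20 on adalimumab. Recalculate the cut-offs for the actual per-protocol n; with 18 on placebo they become 0 or ≥11.
2. Choose the level after looking at both PoC probability and false PoC over placebo rates of 27.6% to 50%. A 5% rule costs little power but barely lowers false PoC when placebo runs high (13.0% to 12.6% at a common 50%).
3. State that this rule alone decides which prior is primary, and that it is applied by staff without interim knowledge.
4. Always report the informative-prior and vague-prior results side by side.
5. Keep the graphs to examine Hurley-stage mismatch or interaction, which a count-based rule cannot see.
6. List the swap in SAP 3.9 and, as a clarification, cross-refer to Beta(0.5, 0.5) in SAP 8.2.3.4. If the Interim Analysis SAP already holds the rule, cross-refer to it instead.

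The cost is a few lines of text and a short program step. With the 5% example, PoC probability is 98.6% instead of 98.7% at the planned rates, and 89.9% instead of 93.4% at 40% vs 70%. With arms of 36 and 18 the pairs are 98.6% and 98.8%, and 90.5% and 94.3%.

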8.2.2.4 Presentation of results from the primary analysis of the primary efficacy variable

The Bayesian analysis will be implemented using multiple chains each utilizing different starting values for the model specified parameters. The posterior samples from each chain will be combined into 1 dataset from which the posterior summaries will be estimated. Missing data will be handled as described in [Section 4.2.1](#).

The posterior distributions of the PBO and BKZ group response rates, and of the difference in response rates between the treatment groups, will be summarized using means, medians, SDs, 95% credible intervals, and 95% highest posterior density intervals. The posterior probability that the difference in response rates between the PBO and BKZ groups is greater than zero (ie, BKZ demonstrates a greater response compared with PBO) will also be presented.

8.2.3 Supportive and sensitivity analyses of the primary efficacy variable

The primary efficacy analysis set is the PPS, however the primary analysis and all supportive and sensitivity analyses of the primary efficacy variable will be repeated using the FAS.

The comparison of the BKZ treatment group to the ADA treatment group is described specifically in this section as a sensitivity analysis, however, it must be noted that the results from the BKZ versus ADA comparison will be presented for completeness in each of the sensitivity analyses described in [Section 8.2.3.1](#) to [8.2.3.10](#) below.

Further analyses of the primary efficacy variable may be performed adjusting for other Baseline covariates. Results from any additional analyses will not be used as a substitute for the planned analyses, but may be used as supplemental information for the CSR. Should such analysis become necessary they will be defined in a further amendment to this SAP.

All sensitivity analyses of the primary efficacy variable are specified in the sections below.

8.2.3.1 Choice of analysis set

The primary analysis of the primary efficacy variable will be repeated for the FAS in order to evaluate the effect that any IPDs may have on the results of the analysis. The analysis and results presentation as specified in [Section 8.2.2.4](#) will be applied

8.2.3.2 Comparison of bimekizumab and adalimumab

In addition to the primary comparison of the BKZ and PBO treatment groups, the comparison between BKZ and ADA in HiSCR at Week 12 will be performed using the methods as described above in [Section 8.2.2.4](#) for the primary efficacy analysis. A 60% credible interval will be presented for the BKZ versus ADA comparison. This will be an informal comparison to assess whether any improvements in response rate observed with BKZ (over PBO) are comparable to the current standard of care (ADA); it will not be part of the evaluation of PoC for this study.

8.2.3.3 Observed case Bayesian analysis

The primary Bayesian analysis of HiSCR at Week 12 will be performed and reported as specified in [Section 8.2.2.4](#) without applying NRI for missing response data, ie, observed case analysis.

8.2.3.4 Vague prior distribution

A sensitivity analysis will be performed to investigate the influence of the choice of prior distribution on the results of the primary analysis. This will be performed and results reported using the same methodology as described in [Section 8.2.2.4](#) but assuming vague priors for all Beta distributed parameters of the model (ie, Beta [0.5, 0.5]).

8.2.3.5 Concomitant antibiotic use – Bayesian analysis

The primary Bayesian analysis of HiSCR at Week 12 will be repeated including treatment group, Baseline Hurley Stage, concomitant antibiotic use at study entry (coded as a binary [yes/no] variable) as an additional covariate, and a concomitant antibiotic use × Baseline Hurley Stage interaction term.

The results of this analysis will be presented as specified in [Section 8.2.2.4](#).

8.2.3.6 Rescue therapy – Bayesian analysis

The primary Bayesian analysis of HiSCR at Week 12 will be performed and reported as specified in [Section 8.2.2.4](#) and will treat subjects who receive specific rescue medication prior to the Week 12 visit as non-responders, from the point of receiving the rescue medication.

